Microbiome study (26) suggested that patients with Th2-low asthma, the same group that responded in the AZISAST study, have a higher microbial burden than patients with the Th2-high phenotype. The AMAZES trial, in contrast, did not distinguish a difference in Th2-high versus Th2-low asthma in the efficacy of azithromycin on exacerbations. Differences in bacterial biomass or composition, all of which may reflect a dysbiotic microbiome, may be one key factor: azithromycin may work in these patients. None of the above-cited studies examined the microbiome, and so a key link to understand how macrolides might benefit patients with poorly-controlled asthma is missing. Neutrophilic asthma, one key Th2-low subtype, is associated with increased bacterial load and pathogens (identified by culture) such as *Hemophilus*, *Pseudomonas*, and *Moraxella* (48). Identifying the correct patient group may be the key to resolving the conflict of whether azithromycin is useful in asthma.

Why would a new study succeed where past, non-selective studies have failed? We hypothesize that in the right asthma phenotype – neutrophil dominant, Th2-low – modifying the dysbiotic microbiome in turn improves clinical control. Our trial will focus on the relation of asthma control to changes in the microbiome induced by azithromycin and understanding the influence of Th2-based phenotypes on this response. By careful examination of the dysbiotic microbiome, careful focus on Th2-low asthmatic patients, and focusing on patients with poor control in which the potential signal is substantial, we will answer the question definitively.

Purpose

The purpose of this protocol is to perform a short-term pilot study so as to acquire data critical to the proper design of a full-scale RCT. The primary objectives of the pilot study are to:

- a) Estimate variability of microbiome composition and diversity over time in control and asthmatic subjects to provide a baseline for the future RCT
- b) Estimate the response of the airway microbiome to azithromycin over time, so that we can generate appropriate power calculations and sample size estimates for the future RCT
- c) Refine our microbial informatics pipeline for the future RCT
- d) Refine our sputum gene expression and cytokine array testing
- e) Test the feasibility of our intervention in a small cohort of subjects with poorly-controlled asthma

Study Design

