4. Diary is completed twice daily by asthmatic subjects at home. Compliance will be reviewed at every visit (clinic or telephone).
5. Peak flow meter readings are done twice daily. Compliance will be reviewed at every visit (clinic or telephone).
6. Reversibility only conducted on those subjects with an $FEV1\% < 60\%$ predicted.
7. Only required for females of child-bearing potential
8. Methacholine challenge only conducted on subjects whose $FEV1\% > 60\%$ predicted.

Inclusion criteria (All participants):

1. Age 18 - 55 years
2. Able to provide informed consent
3. QTc < 440 ms on ECG
4. Smoking history < 10 pack-years

For subjects with poorly controlled asthma

1. Methacholine PC20 ≤ 16 mg/ml
2. Albuterol response $\geq 12\%$ on FEV1 after 4 puffs of albuterol
3. Ability to use combination ICS + LABA
4. Meet definition for Th2-low asthma: peripheral blood eosinophil count < 300 and exhaled nitric oxide level < 30 ppb.

Exclusion criteria:

1. History of allergy or intolerance to any medications used in this study
2. Medication exclusions:
 - a. Current use of medications that prolong QTc interval
 - b. Current use of omalizumab or other anti-IgE therapies
 - c. Current use of anti IL 5 therapies
 - d. Current use of anticoagulants
 - e. Prednisone or other oral steroids within past 3 months
3. Pregnancy or lactation
4. Other respiratory or inflammatory disorders (e.g., sarcoidosis, emphysema)
5. Pre-existing liver disease (AST or ALT $> 10\%$ above the upper limit of normal)
6. Smoking within the last 6 months
7. Exacerbation of asthma in past 3 months
8. Affected by a hearing disorder
9. Clinically significant medical condition (e.g., heart failure, seizure disorder) which may increase risk as determined by study investigator
10. Corrected QT interval > 450 msec. Patients with known cardiac history or prolonged QT interval on a screening EKG are excluded given the small but real potential for macrolide-related side effects (49-54).

Recruitment

Subjects will be recruited from the Pulmonary and General Medicine clinics at the University of Chicago and at Northwestern University. We will also use advertisements including online, flyer and posters.

Duration of protocol

Participation may be up to 14 weeks.

Location where research is to be conducted

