Rescue therapy. This will be done using a standard preparation of albuterol, 90 mcg per inhalation, per the device ProAir or equivalent metered dose inhaler. This device is familiar to most asthmatic subjects. Subjects use this medication when required for relief of acute asthma symptoms. Subjects will keep a diary card of the use of albuterol and provide this card to research staff at each visit.

Initial, thorough training in the use of each device is done during visit #1 by research staff using the Teach To Goal method implemented by the Asthma and COPD research team at the University of Chicago (63-65). Adherence to and proper technique in the use of each medication will be assessed at each visit, and will be recorded on forms by research staff. Subjects have a 24/7 access to one of the study physicians or other member of the research team for any problems associated with the use of these medications.

Subjects are instructed not to use other asthma medications during the study without informing research staff. The research lead physicians ([name], [name]) or other member of the research team will contact primary care providers when necessary to ensure appropriate asthma care throughout the study. Subjects return to their prescribed asthma medication use at the end of the trial.

Study Drug

Azithromycin. We have received an exemption from the U.S. Food and Drug Administration (FDA) for the use of azithromycin in this protocol. The dose, 250 mg daily for 8 weeks, is a dose and regimen used in other lung diseases such as bronchiectasis, COPD, and cystic fibrosis (33-40).

Participants with asthma who complete the four week run-in phase (visit 1 to visit 2) will enroll at visit 2 into the study drug phase. They will receive the study drug, azithromycin (250 mg once a day for 8 weeks) or blinded placebo through the end of visit 4. They will be provided with a study drug diary. When they return at Visit 4 the study staff will collect the study drug bottle and count drug remaining. At the time of the telephone review (visit 5) subjects with asthma will be asked about any side-effects from azithromycin/placebo use.

Subjects are cautioned about potential side-effects of the drug and reminded about how to contact a study physician or other member of the research team.

Payment

Subjects will receive \$100 at the end of each visit for a total of \$400. This will come in a form of a check which will be mailed to their home.

Risks

Azithromycin

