The use of azithromycin is contraindicated in patients with known hypersensitivity to any macrolide or ketolide, or in patients with a history of cholestatic jaundice or hepatic dysfunction associated with prior use of azithromycin.

Common:

- Mild Diarrhea
- Nausea
- Abdominal pain
- Vomiting
- Mild rash
- Nervous feeling

-Sleep problems

Very Uncommon:

- Diarrhea that is watery or bloody
- Headache with chest pain and severe dizziness
- Ototoxicity (hearing loss)
- Fainting
- Fast or pounding heartbeats
- Nausea
- Upper stomach pain
- Itching
- Loss of appetite
- Dark urine
- Clay-colored stool
- Jaundice (yellowing of the skin or eyes); or
- Severe skin reaction -- fever, sore throat, swelling in face or tongue, burning in eyes, skin pain, followed by a red or purple skin rash that spreads (especially in the face or upper body) and causes blistering and peeling

Rare:

Azithromycin is an antibiotic. Like with any other antibiotic, bacteria in the body may develop resistance to the medicine over time. Because of this the body may not fight off these bacteria as well as it should fight them off if these bacteria were to cause an infection. While the practical risk of this is very low, given what we know about azithromycin and resistant bacteria, if the subject were to develop an infection during or immediately after this study such as a bronchitis (infection of the breathing tubes), ear infection, throat infection, or sinus infection, the doctors should treat them with an antibiotic other than azithromycin.

There are known drug interactions with neflifinavir and with warfarin. Previous asthma-related studies using azithromycin have demonstrated few severe adverse events (20,41,44,57,58).

Spirometry:

The spirometry test may cause some study subjects to feel short of breath, lightheaded or dizzy. Treatment will be available if this occurs.

Methacholine challenge testing:

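### Neither eligibility nor the analysis plan deals with recent or non-study antibiotics, which weakens the pilot's microbiome variability and before-after estimates.

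*Combined protocol and SAP*

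**What the plan says.** The Purpose section lists among the primary objectives "Estimate variability of microbiome composition and diversity over time in control and asthmatic subjects to provide a baseline for the future RCT" and "Estimate the response of the airway microbiome to azithromycin over time", the latter to supply power and sample size figures for the later trial.

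The medication exclusions (Exclusion criteria, item 2) cover five classes. Four concern current use only: QTc-prolonging drugs ("Current use of medications that prolong QTc interval"), anti-IgE, anti-IL-5 and anticoagulants. The fifth has a look-back: "Prednisone or other oral steroids within past 3 months". Item 7 also excludes "Exacerbation of asthma in past 3 months". No item names antibiotics, past or current, for either cohort.

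Under Study Drug, "Participants with asthma who complete the four week run-in phase (visit 1 to visit 2) will enroll at visit 2 into the study drug phase". The Schedule of Events collects sputum and oral wash at all four site visits in both cohorts, so asthma subjects give two sets of samples before study drug. It also lists a concomitant medication review at each of those visits.

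The azithromycin text under Risks says that if an infection arises during or just after the study, "the doctors should treat them with an antibiotic other than azithromycin". The Statistical analysis section says nothing about samples taken after such a course.

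**The concern.** The trial rests on the idea that an antibiotic can alter the airway microbiota. An earlier antibiotic course is therefore an exposure of the same kind as the intervention. A subject who finished one shortly before Visit 1 is eligible, and any recovery then appears as change over time unrelated to azithromycin.

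Three quantities are exposed:

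- **Variability over time, objective (a).** Recovery in a few subjects widens the spread of within-subject change. With only 10 controls, one or two affected subjects carry weight.
- **The before-after change under Power calculations.** This estimate has no comparator, so drift adds directly to it, and it is meant to inform the size of the next trial.
- **The azithromycin-placebo contrast.** It gains noise and so loses precision.

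Courses taken during the run-in or the treatment period raise the same problem, and the plan has no rule for those samples.

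**Working it through.** **1. Which safeguards cover what**

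| Safeguard | Covers | Leaves open |
|---|---|---|
| No exacerbation in 3 months | Courses given for an exacerbation | Courses for other infections; all controls |
| No current QTc-prolonging drug | Arguably current macrolides | Completed courses; antibiotics without a QTc effect |
| Four-week run-in, second pre-drug sample at Visit 2 | Puts a course that ended a week before Visit 1 about 1 + 4 = 5 weeks before first dose | Week-0 samples; courses during run-in; controls |
| Concomitant medication review | Records exposure | Triggers no action |

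The value of the run-in depends on which visit is baseline. Outcome Measures defines change from 0 to 8 weeks, and the schedule labels Visit 1 as Week 0. Study drug, however, runs for 8 weeks from Visit 2 to Visit 4. If Visit 2 is the baseline, the run-in helps considerably. If Visit 1 is, the baseline sample precedes it.

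**2. Reproducing the plan's own figures**

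Inputs from Power calculations: abundance 10.4 ± 1.8 (the 1.8 read as an SD), n = 20, two-sided alpha 0.05, 80% power, rho 0.7 or 0.5.

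Variance of change = 2 × 1.8² × (1 − rho):

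- rho 0.7: 1.944, SD 1.394
- rho 0.5: 3.240, SD 1.800

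For a paired t-test with 19 degrees of freedom, the detectable change is 0.6604 × SD:

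- rho 0.7: 0.92 (plan 0.9)
- rho 0.5: 1.19 (plan 1.2)

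The 95% half-widths are 0.65 (plan 0.7) and 0.84 (plan 0.84). The figures reproduce to rounding.

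**3. Sensitivity to recovering baselines**

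The documents give neither the share of subjects affected, q, nor the shift from recovery, m. Assume q of 10% to 20% and m of 1 to 3 percentage points. The added variance is q(1 − q)m². For q = 20% and m = 3 it is 0.2 × 0.8 × 9 = 1.44. At rho 0.7 the SD becomes √(1.944 + 1.44) = 1.840 and the detectable change 0.6604 × 1.840 = 1.21.

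| m | q | Added variance | Detectable change, rho 0.7 | rho 0.5 |
|---|---|---|---|---|
| none | none | 0 | 0.92 | 1.19 |
| 1 | 10% | 0.09 | 0.94 | 1.21 |
| 1 | 20% | 0.16 | 0.96 | 1.22 |
| 2 | 10% | 0.36 | 1.00 | 1.25 |
| 2 | 20% | 0.64 | 1.06 | 1.30 |
| 3 | 10% | 0.81 | 1.10 | 1.33 |
| 3 | 20% | 1.44 | 1.21 | 1.43 |

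A future sample size scales with this variance. The ratio runs from 2.034/1.944 = 1.05 to 3.384/1.944 = 1.74 at rho 0.7, and from 3.33/3.24 = 1.03 to 4.68/3.24 = 1.44 at rho 0.5.

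**4. Drift in the uncontrolled change**

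If the shifts share one direction, the before-after mean moves by q × m, from 0.1 × 1 = 0.1 to 0.2 × 3 = 0.6 points. With no drug effect and rho 0.5, the noncentrality q × m/(SD/√20) runs from 0.1/(1.825/4.472) = 0.25 to 0.6/(2.163/4.472) = 1.24. The nominal 5% paired test would then reject about 6% to 22% of the time.

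**5. Chance of at least one affected subject**

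From 1 − (1 − q)ⁿ: 88% to 99% among 20 azithromycin patients and 65% to 89% among 10 controls, for q of 10% to 20%.

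**The case against.** - **Existing cover is better than the bare list suggests.** This stands for asthma subjects, and most clearly if Visit 2 is the baseline. It does not stand for controls or for courses given for other infections.
- **A reader might infer that the azithromycin-placebo comparison is biased.** The documents do not support that. Exposure before Visit 2 precedes 1:1 randomisation and is balanced in expectation; chance imbalance at 20 per arm is reflected in the standard error. The cost is mainly precision.
- **A reader might take the largest figures as the expected loss.** Nothing supports a 3-point shift, which is 3/1.8 = 1.7 times the stated SD. With a 1-point shift the detectable change rises by only 1% to 4%.
- **Patients on a daily antibiotic may not keep recovering.** This is a fair doubt about applying step 4 to the azithromycin arm. Recovery drift fits the placebo and control groups better, which is why objective (a) is the firmer ground.
- **The pilot's variance should match the future trial's population.** This also stands. If that trial will admit recent antibiotic users, including them here gives the relevant variance. The documents do not say.
- **The infection wording under Risks is conditional.** It is a statement about resistance, not a plan to give antibiotics. It does show that such courses are foreseeable, and the recorded medications would allow a sensitivity analysis. None is specified.

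**Conclusion.** The gap is real and worth closing: there is no antibiotic criterion for either cohort and no rule for samples taken after a non-study antibiotic, in a study with microbiome stability and response to an antibiotic among its primary objectives. It is partly mitigated for asthma subjects and unmitigated at entry for controls.

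The size is uncertain. Under the assumed shares and shifts, the loss in detectable change ranges from negligible to about a third (1.21/0.92 = 1.32) at rho 0.7, and to about a fifth (1.43/1.19 = 1.20) at rho 0.5. These are illustrations, because no exposure rate or recovery size is given. They also assume that 1.8 is an SD, as the plan's own figures imply.

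The point concerns the microbiome objectives. The listed primary outcome measure is the change in ACT score, and nothing here shows that it is compromised. For an explicitly exploratory pilot, this is a change the sponsor should make, not a flaw that invalidates the trial.

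**What to change.** 1. Add systemic antibiotic use before Visit 1 to exclusion 2, for asthma and control subjects alike. The sponsor should justify the window; the 3 months already used for oral steroids and exacerbations is a natural default, but it was not chosen with the microbiome in mind.
2. Record the date of last antibiotic use at Visit 1, and use the existing medication reviews to flag every sample taken after a non-study antibiotic.
3. Prespecify a repeat of the microbiome analysis without the flagged samples.
4. State whether Visit 1 or Visit 2 is the baseline for the microbiome outcomes.

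None of this alters how an infection is treated. The cost is one eligibility line, a short analysis paragraph and slightly slower recruitment. The resulting variance would apply to a future trial with the same exclusion, and the pilot report should say so.

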This pilot protocol examines the change in the airway microbiome after azithromycin over an 8 week period. 40 subjects with poorly controlled asthma and 10 control subjects with no known lung disease will undergo clinical data collection including ACT score, lung function, exhaled nitric oxide (FeNO), methacholine challenge, and induced sputum and blood collection. Participants with asthma then are randomized 1:1 to receive azithromycin, 250 mg, or placebo, daily for 8 weeks. Clinical parameters including ACT, oral wash, adherence, side-effect profile, spirometry, and biological specimens (sputum, blood, FeNO) are collected again at 4 and 8 weeks. Control subjects undergo the same measurements, but do not receive any intervention.

Schedule of Events

	Asthma (A) or Control (C)	Visit 1/Week 0 (Screening) (+/- 3 days)	Visit 2/Week 4 (+/- 3 days)	Week 6 (+/- 3 days)	Visit 3/Week 8 (+/- 3 days)	Week 10 (+/- 3 days)	Visit 4/Week 12 (+/- 3 days)	Week 14 (+/- 3 days)
Informed Consent	A,C	X						
Site Visit	A,C	X	X		X		X	
Phone Call	A			X		X		X
Confirmation of Eligibility	A,C	X	X					
Randomization	A		X					
Drug Dispensation	A	X ^{1,2}	X ^{1,2,3}		X ^{1,2,3}		X ^{1,2}	
Demographics	A,C	X						
Medical History Review	A,C	X						
Asthma History	A	X						
Smoking History	A,C	X						
Concomitant Medication Review	A,C	X	X		X		X	
Physical Exam/Vital Signs	A,C	X	X		X		X	
Asthma Control Test	A	X						
Demographics Questionnaire	A,C	X						
Family History Questionnaire	A,C	X						
Work Exposures Questionnaire	A,C	X						
Home Exposures Questionnaire	A,C	X						
Physical Activity Questionnaire	A,C	X						
Secondhand Smoke Exposure Questionnaire	A,C	X						
Peak Flow Meter Readings ⁵	A	X	X	X	X	X	X	X
Electronic Diary ⁴	A	X	X	X	X	X	X	X
ECG	A,C	X	X		X		X	
Spirometry with Reversibility ⁶	A,C	X	X		X		X	
Exhaled NO	A,C	X	X		X		X	
Urine Pregnancy Test ⁷	A,C	X						
Methacholine Challenge ⁸	A,C	X	X		X		X	
Sputum Induction	A,C	X	X		X		X	
Oral Wash	A,C	X	X		X		X	
Complete Blood Count with Platelet Count and Differential Blood Sample	A,C	X			X			
Serum IgE Blood Sample	A,C	X						
RAST Blood Analysis	A,C	X						
Research Blood Samples	A,C	X			X			
Adverse Events Review	A,C		X	X	X	X	X	X
Compliance/Adherence to Diary and Study Drugs	A	X	X	X	X	X	X	X

1. Dispensation of albuterol to asthmatic subjects (if required at Visit 2 and Visit 3)
2. Dispensation of ICS/LABA to asthmatic subjects
3. Dispensation of azithromycin/placebo to asthmatic subjects

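### During blinded dosing, the infection advice rules out only azithromycin, which is narrower than the entry safeguards, and the Week 6 and Week 10 calls carry no medication review (minor, cheap to improve)

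*Combined protocol and SAP*

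**What the plan says.** **Infection advice.** Under Risks, Azithromycin, the paragraph headed Rare discusses bacterial resistance. It then addresses what should happen "if the subject were to develop an infection during or immediately after this study", giving bronchitis and ear, throat and sinus infections as examples: "the doctors should treat them with an antibiotic other than azithromycin". No other drug or class is ruled out.

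**Entry safeguards.** Exclusion 2a bars "Current use of medications that prolong QTc interval". Exclusion 10 removes people with a known cardiac history or a prolonged QT interval, and gives the side effects of macrolides, not of azithromycin alone, as the reason. Eligibility is confirmed at Visits 1 and 2.

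**Dosing period.** According to the Study Drug section, blinded study drug runs from Visit 2 (Week 4) to Visit 4 (Week 12).

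**Monitoring.** In the Schedule of Events, the row "Concomitant Medication Review" is marked at the four site visits (Weeks 0, 4, 8 and 12) and is blank at the telephone calls. The row "Adverse Events Review" is marked at Visits 2 to 4 and at the calls in Weeks 6, 10 and 14. An ECG is done at every site visit.

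**Instructions to subjects.** The section on asthma medications states: "Subjects are instructed not to use other asthma medications during the study without informing research staff". The Study Drug section adds that subjects are cautioned about side effects and "reminded about how to contact a study physician or other member of the research team".

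**The concern.** Exclusion 2a keeps a particular combination, azithromycin with another QT-prolonging drug, out of the trial at entry. The infection advice applies while subjects may be taking azithromycin, yet its wording reflects resistance only. A prescriber who followed it exactly could choose another macrolide or a QT-prolonging antibiotic. The illnesses it names are ordinary ones that a doctor outside the study may well treat.

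The timing of medication review adds to this. A new drug is asked about directly only at site visits four weeks apart, although staff already telephone subjects midway between those visits. At stake is the safety of the roughly 20 subjects on azithromycin. Treatment is blinded, so any precaution has to cover all 40 randomized subjects.

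**Working it through.** **Step 1. Does the advice cover dosing?** It applies during the study as well as just after it. Dosing occupies Weeks 4 to 12, so the answer is yes.

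**Step 2. How does the advice compare with the entry rules?**

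| Drug added to study drug | Entry rules | Infection advice |
|---|---|---|
| Azithromycin | Covered by the macrolide concern in exclusion 10 | Ruled out |
| Another macrolide | Covered by the same concern in exclusion 10 | Not mentioned |
| Any other QT-prolonging antibiotic | Current use barred by 2a | Not mentioned |

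The advice matches the entry rules only in the first row. The protocol does not list which antibiotics prolong QTc, and none needs to be named for the mismatch to hold.

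**Step 3. Spacing of medication review during dosing.** Inputs from the Schedule of Events: site visits at Weeks 4, 8 and 12, each with a window of 3 days either side.

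- Nominal gap: (8 − 4) × 7 = 28 days, and the same from Week 8 to Week 12. This is the plan's own four-week spacing.
- Range: 28 − (3 + 3) = 22 days to 28 + (3 + 3) = 34 days.

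**Step 4. Spacing if the Week 6 and Week 10 calls also carried the review.** The calls have the same 3-day window.

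- Nominal gap: (6 − 4) × 7 = 14 days.
- Range: 14 − 6 = 8 days to 14 + 6 = 20 days.
- Reviews over Weeks 4 to 12: 3 now (Weeks 4, 8, 12), and 5 with the calls (Weeks 4, 6, 8, 10, 12).

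Adverse event review already runs at the 14-day spacing.

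**Step 5. Who is affected?** 40 subjects randomized 1:1 gives 40 / 2 = 20 on azithromycin.

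**Step 6. Added workload.** 40 subjects × 2 calls = 80 questions at most. The protocol gives no time per question. Assuming 2 to 5 minutes each, the total is 80 × 2 / 60 = 2.7 hours to 80 × 5 / 60 = 6.7 hours, before data entry.

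**What cannot be calculated.** The protocol gives no rate of infection, antibiotic use or QT events. The gain in detection cannot be quantified, because adverse event review at the same calls would already reveal some of these drugs.

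**The case against.** The strongest reply is that the sentence is a risk disclosure about resistance. It explains why azithromycin would be a poor choice for a new infection; it is not a list of permitted drugs. That is a fair account of its purpose, and it would be wrong to read the sentence as authorizing other macrolides. It is nevertheless worded as advice to treating doctors, and someone relying on it would not learn of the QT concern stated elsewhere.

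Second, contact is more frequent than the 28-day figure suggests. Adverse events are reviewed about every 14 days, and the listed infections are what such a review would be expected to elicit. The twice-daily symptom diary and the contact reminder are further routes by which an illness could surface. This largely stands. A reader might infer that a treated infection would go unnoticed until the next site visit; the schedule does not support that as a general statement. What remains is a drug started without a reported event, since neither the adverse event row nor the listed diary content is a question about new medicines.

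Third, safety rules may sit elsewhere. The section on the Data and Safety Monitoring Board places the DSMP in Appendix 1, and neither it nor the consent pages were available. This also stands. A reader might infer, from the "current use" style of the exclusions and from the on-study instruction being limited to asthma medications, that the plan has no rule for QT-prolonging drugs or anticoagulants started later, or for holding study drug. The available text cannot establish that. The anticoagulant argument is weak in any case: the protocol gives no reason for exclusion 2d, and the remark "There are known drug interactions with neflifinavir and with warfarin" is a separate risk statement. An unseen appendix would not, however, change the narrow wording of the advice or the two blank cells in the schedule.

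**Conclusion.** The point holds as a minor safety improvement. During blinded dosing the infection advice is narrower than the protocol's own entry safeguards, and direct medication review is 28 days apart (22 to 34) when existing calls would allow 14 days (8 to 20).

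Absolute risk is likely small. Subjects are aged 18 to 55, must meet a QTc limit, have no known cardiac history, and have ECGs at Weeks 4, 8 and 12. About 20 take azithromycin. No event rate is given and none is estimated. The primary outcome analysis is unaffected.

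The conclusion rests on the wording of the Risks section and the marks in the Schedule of Events. It does not depend on what the DSMP or the consent pages say about anticoagulants or holding study drug, and it makes no claim about either.

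**What to change.** 1. In the Schedule of Events, mark medication review at the existing Week 6 and Week 10 calls for subjects with asthma.
2. In the Risks section, revise the advice so that while a subject is on study drug, in either arm, an infection is treated with an antibiotic that is not azithromycin, another macrolide or another QT-prolonging agent, where a suitable alternative exists. State that urgent treatment is not to be delayed. If the DSMP or the consent form already says this, align the wording and add a cross-reference.

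The cost is a wording change and at most 80 added questions on calls already planned: 2.7 to 6.7 staff hours in total on the assumed 2 to 5 minutes each. Data entry comes on top and is not priced here; the protocol uses double entry and keeps paper forms. The other downside is a somewhat narrower choice of antibiotic, including for subjects who are in fact on placebo. Neither change requires unblinding.

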Long-acting beta agonist therapy (salmeterol): Common: headache, dizziness, lightheadedness, insomnia, nausea, dry mouth and throat irritation.

Short-acting beta agonist therapy (albuterol): Common: nervousness, shaking of a part of the body, headache, irritation of the throat, cough, and muscle, bone or back pain.

Pregnancy

Women of childbearing potential will undergo a pregnancy test on the day of study entry and at each visit. They must have a negative urine pregnancy test to be eligible for study entry. If the

test is positive, the study physician will discuss the matter with the participant. If a participant becomes pregnant before completing the study, they will be asked to notify one of the study doctors immediately. The investigator shall counsel the subject and discuss the risks of continuing with the pregnancy and the possible effects on the fetus. Monitoring of the pregnant subject shall continue until the conclusion of the pregnancy. Pregnancies will be reported to the data and safety monitoring board (DSMB) within one day of the site's awareness. Should the pregnancy result in a congenital abnormality or birth defect, a SAE will be submitted to the IRB, DSMB and NHLBI using the SAE reporting procedures described below.

Confidentiality

Each subject will be assigned a sequential identification number. This number will be linked to the subjects name and data.

We maintain strict confidentiality of all data to minimize the risk of inappropriate access or dissemination of such information. All protected health information including genotype data is saved on a password-protected computer or CRI server in a locked office with limited access. Only staff listed on this protocol will have access to the subjects name and data.

Data sent outside the University of Chicago or Northwestern University, will be sent using an identification number and not the participant's name.

Outcome Measures

Primary:

- ✓ ACT score change from 0 (baseline) to 8 weeks

Secondary:

- ✓ Change in FEV1 from 0 (baseline) to 8 weeks
- ✓ Sputum eosinophils change from 0 (baseline) to 8 weeks
- ✓ Sputum neutrophils change from 0 (baseline) to 8 weeks
- ✓ COMPEX score of asthma severity (from daily diary)
- ✓ Microbiome Shannon alpha-diversity score change from 0 (baseline) to 8 weeks
- ✓ Microbiome beta-diversity score change from 0 (baseline) to 8 weeks
- ✓ Microbiome change in relative proportion of top 10 genera from 0 (baseline) to 8 weeks

Data management

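### The Pregnancy section requires a test at every visit, but the Schedule of Events marks one only at Visit 1, so neither visit that dispenses study drug has a test marked

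*Combined protocol and SAP*

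**What the plan says.** The Pregnancy section, which follows the risk statements, sets the testing rule: "Women of childbearing potential will undergo a pregnancy test on the day of study entry and at each visit". It makes a negative urine test a condition of study entry. It also asks a participant who becomes pregnant during the study to tell a study doctor.

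The Schedule of Events has a row for "Urine Pregnancy Test" with a single mark, at Visit 1 (Week 0). Its only footnote, number 7, reads "Only required for females of child-bearing potential".

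Four other statements bear on the timing:

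- The Drug Dispensation row carries footnote 3, "Dispensation of azithromycin/placebo to asthmatic subjects", at Visits 2 and 3 only.
- The Study Drug section says that participants with asthma who finish the four-week run-in "will enroll at visit 2 into the study drug phase".
- The row "Confirmation of Eligibility" is marked at Visits 1 and 2, and randomisation is marked at Visit 2.
- Exclusion criterion 3 is "Pregnancy or lactation".

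**The concern.** Two current parts of the protocol give different instructions for the same safety test, and no rule says which prevails. Study coordinators commonly work from the schedule, and anyone doing so here would omit tests that the text requires.

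The omitted tests include those at both visits where study drug is handed out. Visit 2 matters most: participants are randomised there and eligibility is checked again. A known pregnancy would bar randomisation, but the schedule marks no test to detect an unrecognised one. After Visit 2, a site using the schedule alone would depend on the participant reporting a pregnancy herself. The listed eligibility criteria contain no contraception requirement that would lower the chance of one.

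What is at stake is avoidable exposure to study drug in early pregnancy. The Risks section describes that risk in moderate terms: FDA category B, adequate controlled studies in pregnant women lacking, and use in pregnancy advised only where there is a clear need.

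**Working it through.** The protocol states no figure to reproduce. The check sets the text against the schedule and counts visits and days.

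**Number of visits.** The schedule marks four site visits, at Weeks 0, 4, 8 and 12. The Payment section agrees: $400 in total at $100 per visit gives 400 / 100 = 4. The telephone contacts at Weeks 6, 10 and 14 cannot include a urine test at the site, so the rule in the text means four tests.

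**Text against schedule.**

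| | Visit 1 (day 0) | Visit 2 (day 28) | Visit 3 (day 56) | Visit 4 (day 84) |
|---|---|---|---|---|
| Test required by the Pregnancy section | yes | yes | yes | yes |
| Test marked in the Schedule of Events | yes | no | no | no |
| Eligibility confirmed | yes | yes | no | no |
| Study drug dispensed (footnote 3) | no | yes | yes | no |

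- Tests marked: 1 of 4 site visits.
- Dispensing visits with a test marked: 0 of 2.

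**Is the gap a table-reading artefact?** Probably not. The row directly above (exhaled nitric oxide) and the row directly below (methacholine challenge) each keep all four marks. The pregnancy row has the same layout as other rows meant for Visit 1 only, such as serum IgE.

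**Does the meaning of study entry resolve it?** No. If entry is Visit 1, the text still requires tests at Visits 2 to 4. If entry means joining the study drug phase at Visit 2, the schedule omits the entry test itself.

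**Age of the only marked result if the schedule alone is followed.**

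- At first dose: 28 − 0 = 28 days. If the ±3-day windows at Visits 1 and 2 vary independently, the range is 28 ± 6, or 22 to 34 days. If Visit 1 is taken as day 0, it is 28 ± 3, or 25 to 31 days.
- At the end of dosing (Visit 4): 84 − 0 = 84 days. The corresponding ranges are 84 ± 6, or 78 to 90 days, and 84 ± 3, or 81 to 87 days.
- Nominal dosing period: 84 − 28 = 56 days, all of it after the only marked test.

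**Number exposed.** Forty participants with asthma are randomised 1:1, so 40 / 2 = 20 receive azithromycin. The documents do not say how many will be women of childbearing potential.

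**The case against.** The strongest reply is that the safeguard is already in the protocol in plain words, and that only marks in a summary table are missing. Pregnancy is an exclusion, eligibility is reconfirmed at Visit 2, and pregnancies must be reported to the DSMB within one day of the site becoming aware. Every consequence above depends on staff overlooking the text, and nothing in the documents shows that they would. On this view it is a clerical correction.

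That reply limits the size of the problem but does not remove it. The schedule is an operative instruction, and a site following either part departs from the other. Reconfirming the exclusion at Visit 2 detects only a pregnancy already known, and the reporting rule starts only once the site is aware.

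Three narrower points have some force:

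- The drug-exposure argument supports tests at Visits 2 and 3 in participants with asthma. Testing at Visit 4, and testing controls, who receive no intervention, rests only on agreement with the text.
- Requiring a negative result before dispensing goes beyond aligning the two parts. The Data Safety and Monitoring Plan may already contain such a rule. It and the SAE procedures to which the Pregnancy section refers were not available, so this cannot be judged. Neither could make the two protocol statements agree.
- The wider day ranges assume that both visit windows vary. The conclusion needs only the nominal 28 and 84 days.

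**Conclusion.** The inconsistency is real, and nothing in the available text resolves it: four tests required, one marked, and none marked at the two dispensing visits. It should be fixed. If only the schedule were followed, women of childbearing potential would be randomised and started on study drug on a result nominally 28 days old, and would complete 56 days of dosing with no further test.

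This is a participant-safety and operational matter, modest in scale given about 20 azithromycin recipients of both sexes and the protocol's moderate risk statement. It does not affect sample size, power, alpha or the analysis. The conclusion assumes that the schedule as read is complete, which the neighbouring rows support. The stated consequences are conditional on staff following the schedule rather than the text.

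**What to change.** Mark the urine pregnancy test at Visits 2, 3 and 4 in the Schedule of Events, keeping footnote 7. State that a negative result is required before study drug is dispensed at Visits 2 and 3, unless the Data Safety and Monitoring Plan already says so.

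The cost is one clarifying amendment to a table row. Relative to the schedule it adds up to three urine tests per woman of childbearing potential, at visits already planned; relative to the text it adds none. The number of such women is not given, so the total lies between 0 and 3 × 50 = 150 (3 × 40 = 120 for asthma participants and 3 × 10 = 30 for controls). Sample size, visits and analysis do not change.

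A minor, unrelated wording point could go in the same amendment. Inclusion criterion 3 requires a QTc below 440 ms, while exclusion criterion 10 and the ECG procedure use a limit of 450 ms. The stricter inclusion limit governs when both lists are applied, so eligibility is unaffected, but a single value would be clearer.
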